menses]) and must use adequate birth control throughout the study period. Adequate birth control is defined as hormonal – oral, implantable, injectable, or transdermal contraceptives; mechanical – spermicide in conjunction with a barrier such as condom or diaphragm; IUD; or surgical sterilization of partner. For non-sexually active females, abstinence may be regarded as an adequate method of birth control.

In the event a female has a positive urine pregnancy test at Visit 4, the subject will be withdrawn from the study and the investigator will notify [REDACTED] and the sponsor within 24 hours of knowledge of the positive pregnancy test.

Methods for Assignment to Treatment Groups

Each subject who signs an ICF will be assigned a subject number. Subject numbers will be assigned in sequential order beginning with 001. Once a subject meets all qualification criteria at Visit 2, he/she will be randomized in a 1:1 ratio via an Interactive Response Technology (IRT) system to one of the following treatment groups: 1: CSF-1 (pilocarpine hydrochloride 0.4% ophthalmic solution), 2: Vehicle, and stratified by iris color (brown versus light [i.e., blue, green, gray, and hazel]) and by baseline manifest refraction spherical equivalent (-4.5 D to <-0.5 D, -0.5 D to +0.75 D, and >+0.75 D to +2.0 D); randomization will not be stratified by site.

At least approximately 30% of subjects will have light (i.e., blue, green, gray, and hazel) iris and at least approximately 30% will have a brown iris. The actual percentages will vary based on enrollment.

Randomization will be used to avoid bias in the assignment of subjects to treatment, to increase the likelihood that known and unknown subject attributes (e.g., iris color and baseline characteristics) are evenly balanced across treatment groups, and to enhance the validity of statistical comparisons across treatment groups. Double-masked treatment will be used to reduce the potential of bias during data collection and the evaluation of clinical endpoints.

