10.7 Efficacy Analysis

Primary Efficacy Analyses

The primary efficacy endpoint in this study is the percentage of subjects with a ≥ 3 -line (15-letter) gain, from baseline, in best distance-corrected visual acuity (BDCVA) at 40 cm (Precision Vision chart) and no loss in best distance corrected visual acuity ≥ 5 letters (ETDRS chart) at Visit 3, 1 hour following Dose 1 in the study eye. The primary efficacy analysis will be conducted in the FAS with intercurrent events handled in the following manners:

- 1) Discontinuation of study drug and non-optimal compliance will be ignored [treatment policy strategy].
- 2) Withdrawal due to lack of efficacy or adverse events: missing data will be singly imputed as failure [hypothetical strategy].
- 3) Missing data without withdrawal or withdrawal due to reasons other than lack of efficacy or adverse events: missing data will be imputed employing Multiple Imputation (MI) using randomized treatment-based Markov Chain Monte Carlo (MCMC) methodology [hypothetical strategy].

No subject data will be excluded from the FAS due to protocol violations/deviations. The FAS will be used for the primary efficacy analyses. Note that multiple imputations of missing values will be completed for the continuous measures (BDCVA at 40 cm and best distance corrected VA at 4m), then the response variable will be determined therefrom.

[REDACTED]

Descriptive statistics will be presented by treatment group. Testing of the percentage of subjects with at least a 3-line (15-letter) improvement from baseline in BDCVA at 40 cm without a loss of ≥ 5 letters in best distance corrected VA at 4m will be completed separately for the 1 hour and 2 hour time points using a generalized linear mixed model with a binomial distribution including fixed effects of baseline BDCVA at 40 cm as a covariate, daily dose (Dose 1 and Dose 2), treatment, and the interaction of dose with treatment and random effect of subject to account for the correlation within a subject between daily doses. [REDACTED]

[REDACTED]

The adjusted odds ratios and marginal proportions and difference in proportions along with corresponding two-sided 95% Confidence Intervals (CIs) and p-values will be presented.

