Treatment comparisons will also be made separately for each time point and dose using logistic regression model including fixed effects of baseline BDCVA at 40 cm as a covariate and treatment, Pearson's chi-squared test or Fisher's exact test if any of the cell counts are less than five as a sensitivity analysis to the primary model above.

Secondary Efficacy Analysis

For the secondary efficacy endpoints of BDCVA at 40 cm, the percentage of subjects who achieve a ≥ 3 -line (15-letters) improvement from baseline without a loss of ≥ 5 letters in best distance corrected VA at 4m for each Visit, time point and daily dose (Dose 1 and Dose 2) will be summarized and analyzed using the same imputation as the primary efficacy endpoint. The same modeling strategy will be used as detailed in the primary efficacy analysis for any time point that is measured after both doses within the visit [e.g.: 2 hours at Visit 3 (Day 8); 30 minutes, 1 and 2 hours at Visit 2 (Day 1); and 20 minutes, 1, 2, and 3 hours at Visit 4 (Day 15)]. For those time points that are measured only after the second dose within the visit [REDACTED]

[REDACTED]

[REDACTED]

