4.1 Method of Assigning Subjects to Treatment Groups

Each subject who signs an informed consent form (ICF) will be assigned a subject number. Subject numbers will be assigned in sequential order beginning with 001. Once a subject meets all qualification criteria at Visit 2 (Day 1), they will be randomized in a 1:1 ratio via an Interactive Response Technology (IRT) system to one of the following treatment groups: (1) CSF-1 or (2) Vehicle, and stratified by iris color (brown versus light [i.e., blue, green, gray, and hazel]) and by baseline manifest refraction spherical equivalent <-0.5 D, -0.5 D to +0.75 D, and >+0.75 D); randomization will not be stratified by site.

At least, approximately, 30% of subjects will have a light iris and at least, approximately, 30% will have a brown iris. The actual percentages will vary based on enrollment.

Randomization will be used to avoid bias in the assignment of subjects to treatment, to increase the likelihood that known and unknown subject attributes (e.g., iris color and baseline characteristics) are evenly balanced across treatment groups, and to enhance the validity of statistical comparisons across treatment groups. Double-masked treatment will be used to reduce the potential of bias during data collection and the evaluation of clinical endpoints.

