12.1 Primary and Key Secondary Efficacy Analysis

The primary efficacy endpoint in this study is the percentage of subjects with a ≥ 3 -line (15-letter) gain, from baseline, in best distance-corrected visual acuity (BDCVA) at 40 cm (Precision Vision chart) and no loss in BDCVA ≥ 5 letters (ETDRS chart) at Visit 3, 1 hour following Dose 1 in the study eye. The key secondary efficacy endpoints are defined the same as the primary efficacy endpoint, except for being measured at 2 hours following Dose 1, 1 hour following Dose 2, and 2 hours following Dose 2, all at Visit 3.

The primary and key secondary efficacy analysis will be conducted in the FAS with missing data handled in the following manners:

1. Discontinuation of study drug and non-optimal compliance will be ignored [treatment policy strategy].
2. Withdrawal due to lack of efficacy or AEs: missing data will be singly imputed as failure [hypothetical strategy].
3. Missing data without withdrawal or withdrawal due to reasons other than lack of efficacy or AEs: missing data will be imputed employing Multiple Imputation (MI) using randomized treatment-based Markov Chain Monte Carlo (MCMC) methods.

No subject data will be excluded from the FAS due to protocol violations/deviations. The multiple imputation of missing values will be completed for the continuous measures (BDCVA at 40 cm and BDCVA at 4 m), then the response variable will be determined therefrom. Imputation of failure due to lack of efficacy or AE will be assigned after multiple imputation is performed.

Variables for treatment group, baseline for BDCVA at 40 cm and baseline for BDCVA at 4 m will also be included in the multiple imputation model. 25 complete imputed datasets will be created.

Example SAS® code for the multiple imputation:

```
PROC MI DATA=DATAIN OUT=MI NIMPUTE=25 SEED=118787 minimum=-0.3 maximum=1;
  MCMC INITIAL=EM;
  VAR TRTPN VA40 VA40BL VA4 VA4BL;
RUN;
```

Where TRTPN = treatment group, coded 1 for CSF-1, else 0

VA40 = value of BDCVA at 40 cm for Visit 3, 1 hour after Dose 1

VA40BL = baseline value of BDCVA at 40 cm

VA4 = value of BDCVA at 4 m for Visit 3, 1 hour after Dose 1

VA4BL = baseline value of BDCVA at 4 m

For each imputed dataset, a logistic regression model with baseline BDCVA at 40 cm as a covariate and treatment as a main effect will be used to obtain the treatment effect estimate, odds ratio, and 95% confidence interval (CI) for odds ratio.

Example SAS® code for the logistic model is shown here:

```

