12.2 Sensitivity Analysis for Primary and Key Secondary Efficacy Endpoints

Sensitivity Analysis for the primary and key secondary efficacy endpoints include:

1. All missing data imputed as failure using the FAS
2. Observed data only using the FAS

[figure not shown]
3. Observed data only using the PPS
4. Missing data will be imputed employing tipping point approach. The analysis will be based on the FAS

[figure not shown]
For #1, #2 and #3 sensitivity analyses, the analysis of primary and key secondary efficacy endpoints will be performed using a logistic regression model with baseline BDCVA at 40 cm as a covariate and treatment as a main effect. The odds ratio, and 95% confidence interval (CI) for odds ratio will be provided. p-values will be presented for the main effect of treatment group using a Wald statistic.

Tipping Point Analysis of Primary and Key Secondary Efficacy Variables

Missing primary and key secondary efficacy endpoint values (i.e., binary response values) will be imputed using tipping point approach. First set all records in CSF-1 with missing value as failures and all records in Vehicle with missing value as successes, that is the worst case. The imputed data will be analyzed using a logistic regression model with baseline BDCVA at 40 cm as a covariate and treatment as a main effect. The p-value, odds ratio, and 95% confidence interval (CI) for odds ratio will be provided. If the p-value is less or equal to 0.05 for the worst case, then stop there. If the p-value is greater than 0.05 for the worst case, then set the missing records as failures or successes in all possible combinations from worse case to the best case until the p-value turns from >0.05 to ≤ 0.05 .

14. Safety Analyses

All safety analyses will be conducted using the SAF. In addition to AEs, BCVA at distance under normal and low-luminance testing conditions, findings from slit-lamp biomicroscopy examination, conjunctival redness grading, study drug drop comfort assessment, dilated indirect fundoscopy, and IOP measurements will be summarized descriptively using quantitative and qualitative summary statistics by treatment arm and subject visit, as appropriate. All such measurements related to safety endpoints will also be presented in a detailed subject listing.

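### Randomisation is stratified by iris colour and MRSE, but no visible efficacy model includes either; adding the strata is a cheap, low-severity improvement that could help only an endpoint with a smaller effect than planned

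*SAP*

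**What the plan says.** SAP 4.1 has subjects randomised 1:1, "stratified by iris color (brown versus light [i.e., blue, green, gray, and hazel]) and by baseline manifest refraction spherical equivalent", the latter in three categories. Protocol 8.1 describes the same scheme and adds that "randomization will not be stratified by site". That makes 2 x 3 = 6 strata. Among the purposes of randomisation, SAP 4.1 lists making it more likely that "known and unknown subject attributes (e.g., iris color and baseline characteristics) are evenly balanced across treatment groups".

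The visible efficacy models are these:

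- **SAP 12.1, primary and key secondary:** "a logistic regression model with baseline BDCVA at 40 cm as a covariate and treatment as a main effect will be used". The example code has the same two terms.
- **SAP 12.2, sensitivity analyses 1 to 3:** "performed using a logistic regression model with baseline BDCVA at 40 cm as a covariate and treatment as a main effect". The tipping-point analysis uses the same model.
- **Protocol 10.7, primary:** a "generalized linear mixed model with a binomial distribution including fixed effects of baseline BDCVA at 40 cm as a covariate", with terms for dose, treatment, their interaction and subject.
- **Protocol 10.7, sensitivity:** a "logistic regression model including fixed effects of baseline BDCVA at 40 cm as a covariate and treatment", plus chi-squared or Fisher tests.

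In the visible SAP, iris colour and MRSE are otherwise only summarised (10.1) or listed (10.2). The outer MRSE categories stop at -4.5 D and +2.0 D in protocol 8.1 and are open-ended in SAP 4.1. The inner cut points, -0.5 D and +0.75 D, agree.

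**The concern.** Stratifying balances the arms on the factors and so removes part of the chance variation in the treatment comparison. A model without those factors does not credit that. If the factors predict response, its standard error is too large for the design: the test rejects less often than 5% under the null and gives up some power.

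Power is what is at stake. SAP 8.5 tests the key secondaries in fixed order: H02 (2 hours after Dose 1), H03 (1 hour after Dose 2), H04 (2 hours after Dose 2). A miss on H02 ends formal inference for the other two.

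**Working it through.** **1. The plan's own figure.** Inputs from protocol 10.5 and SAP 5: n = 140 per arm, 42.5% v 17.5%, two-sided alpha 0.05, Pearson chi-squared.

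Power = Φ{[Δ − 1.96·√(2p̄(1−p̄)/n)] / √[(p1(1−p1) + p2(1−p2))/n]}

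With Δ = 0.25 and p̄ = 0.30, the null SE is √(0.42/140) = 0.0548 and the alternative SE is √(0.38875/140) = 0.0527. Power = Φ[(0.25 − 0.1074)/0.0527] = 99.66%. The stated figure, above 97.5%, holds. It covers 1 hour after each dose, so H01 and H03.

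**2. Where there is room for a gain.** The same formula with lower CSF-1 rates, all assumed, against 17.5%:

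| CSF-1 rate | 40% | 37.5% | 35% | 32.5% | 30% |
|---|---|---|---|---|---|
| Power | 98.8% | 96.7% | 91.9% | 83.0% | 69.3% |

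**3. Simulation.** 280 subjects, permuted blocks of 4 within six strata, logistic outcomes calibrated to the marginal rates, baseline acuity odds ratio (OR) 1.5 per SD. The planned model, logit P(response) = b0 + b1·treatment + b2·baseline, is compared with the same model plus iris (1 df) and MRSE (2 df). The test is the Wald test of b1.

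The documents give no block size, stratum shares or stratum effects, so these are assumptions. Two sets of shares were used:

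- **Set A:** light/brown iris 40/60, MRSE 30/45/25%; 40,000 trials per cell (20,000 at the planning rates).
- **Set B:** iris 55/45, MRSE 30/50/20%; 20,000 null trials, 15,000 for power (3,000 at the planning rates).

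Stratum effects are written as iris OR + MRSE OR per step.

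**Type I error, planned v adjusted** (17.5% in both arms; Monte Carlo SE 0.1 to 0.15 point):

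| Effects | Set A | Set B |
|---|---|---|
| None | 5.0 v 5.1% | 4.8 v 4.9% |
| 1.5 + 1.5 | not run | 4.4 v 4.8% |
| Iris 2 only | 4.6 v 4.8% | not run |
| Iris 3 only | 4.4 v 5.0% | not run |
| 2 + 1.5 | 4.5 v 5.0% | not run |
| 3 + 2 | 4.0 v 5.0% | 3.9 v 4.8% |

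A shorter run of 6,000 trials with strong effects gave about 4.5 v 5.5%. Its SE is √(0.05·0.95/6000) = 0.3 point, so that 5.5% is compatible with 5%.

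**Power at 42.5% v 17.5%.** Both models exceed 99.6%. The gain is at most 0.03 point in set A and 0.04 point in set B (99.73 to 99.77% with 3 + 2).

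**Power at assumed lower rates, raw gain from adjusting, in points:**

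| Effects | 30%, set A | 30%, set B | 35%, set B |
|---|---|---|---|
| None | 0.4 | 0.3 | 0.1 |
| 1.5 + 1.5 | not run | 1.0 | 0.5 |
| Iris 2 only | 1.0 | not run | not run |
| Iris 3 only | 2.2 | not run | not run |
| 2 + 1.5 | 1.7 | not run | not run |
| 3 + 2 | 3.6 | 3.6 | 1.3 |

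Further runs gave 0.5 to 3.9 points at 30% and 0.2 to 1.5 at 35%. Part of each raw gain is the 0.1 to 0.4 point that appears with no stratum effect at all. An extreme 4 + 3 gave 5.4 points at 30% (71.9 to 77.3%, 3,000 trials), so 4 points is not a ceiling.

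**Effects under CSF-1 only.** These runs assume the same stratum effect in both arms. If the strata matter only under CSF-1, the 3 + 2 gain at 30% falls to about 1.2 to 1.4 points.

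**4. Effect on the estimate.** At the planning rates in set A, adjustment moves the odds ratio from 3.67 to 3.94 (2 + 1.5) or from 3.64 to 4.28 (3 + 2). The standardised difference stays at 25.0 points.

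**The case against.** The strongest reply is that the benefit rests on numbers the documents do not contain. No 2-hour rate is visible, and neither document says how prognostic iris colour or MRSE is. Acuity is tested with best distance correction (SAP 2.1), so MRSE may add little. At milder rates, or with effects under CSF-1 only, the gain shrinks. All of this stands, and it is why the gain is given as a conditional range.

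It can also be said that a supportive analysis would be enough. For H01 and H03 at the planning rates, that is fair. It would not recover power for H02 or H04, because the formal test would stay unadjusted.

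Four stronger readings are tempting, and none is supported:

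- **A reader might infer that the omission undermines validity.** It does not inflate type I error; the error runs in the conservative direction.
- **A reader might infer that the key secondaries are weaker than the primary.** H03 has the same planning rates as H01. The protocol labels the 2-hour endpoints as duration of action, which may suggest waning, but it gives no figure.
- **A reader might infer that the SAP dropped factors the protocol had.** Both protocol 10.7 models omit them too.
- **A reader might infer that the imputation code, "VAR TRTPN VA40 VA40BL VA4 VA4BL", must also change.** With 5% missing data, adding the strata there was worth a further 0.1 to 0.4 point, which is negligible.

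Some text is also unseen: no SAP section 13 is visible, SAP 16 on changes from the protocol shows no text, and part of the sample-size section is redacted.

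**Conclusion.** The point holds as a low-severity improvement. The strata are absent from every visible efficacy model. If they are prognostic, the planned test runs at about 4 to 4.5% with strong effects instead of 5%, so a positive result is safe.

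The power gain is nil for H01 and H03 at the planning rates. For an endpoint with an assumed CSF-1 rate of 30 to 35% against 17.5%, it is about 0 to 4 points for stratum effects up to OR 3 + 2. It is near zero without a prognostic effect and smaller if the effect exists only under CSF-1. Whether H02 or H04 is such an endpoint cannot be told from the visible text.

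**What to change.** Before unmasking:

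1. Add the iris stratum (two levels) and MRSE stratum (three levels), as recorded in the randomisation system, as fixed main effects to the logistic models in SAP 12.1 and 12.2. At minimum, add one supportive stratum-adjusted analysis of H01 to H04. Using the recorded strata avoids needing a brown/light rule for eyes that SAP 10.1 classes as heterochromia.
2. Report the standardised difference in proportions with a 95% CI beside the odds ratio, because the adjusted odds ratio is conditional on the strata. The difference is the scale of the hypotheses in SAP 2.6. Protocol 10.7 lists it, but visible SAP 12.1 does not, and SAP 1 says that its methods supersede the protocol's.
3. Align the outer MRSE bounds between protocol 8.1 and SAP 4.1.

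Leave the imputation model as it is.

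The cost is SAP wording, two class variables and one extra output. The three added parameters compare with 140 x (0.425 + 0.175) = 84 expected responders at the planning rates, or about 66 at 30% v 17.5%. No new data are collected, since the randomisation system must already hold the strata. If text not shown already adjusts for them, nothing need change.

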12.2 Sensitivity Analysis for Primary and Key Secondary Efficacy Endpoints

Sensitivity Analysis for the primary and key secondary efficacy endpoints include:

1. All missing data imputed as failure using the FAS
2. Observed data only using the FAS

[figure not shown]
3. Observed data only using the PPS
4. Missing data will be imputed employing tipping point approach. The analysis will be based on the FAS

[figure not shown]
For #1, #2 and #3 sensitivity analyses, the analysis of primary and key secondary efficacy endpoints will be performed using a logistic regression model with baseline BDCVA at 40 cm as a covariate and treatment as a main effect. The odds ratio, and 95% confidence interval (CI) for odds ratio will be provided. p-values will be presented for the main effect of treatment group using a Wald statistic.

Tipping Point Analysis of Primary and Key Secondary Efficacy Variables

Missing primary and key secondary efficacy endpoint values (i.e., binary response values) will be imputed using tipping point approach. First set all records in CSF-1 with missing value as failures and all records in Vehicle with missing value as successes, that is the worst case. The imputed data will be analyzed using a logistic regression model with baseline BDCVA at 40 cm as a covariate and treatment as a main effect. The p-value, odds ratio, and 95% confidence interval (CI) for odds ratio will be provided. If the p-value is less or equal to 0.05 for the worst case, then stop there. If the p-value is greater than 0.05 for the worst case, then set the missing records as failures or successes in all possible combinations from worse case to the best case until the p-value turns from >0.05 to ≤ 0.05 .

14. Safety Analyses

All safety analyses will be conducted using the SAF. In addition to AEs, BCVA at distance under normal and low-luminance testing conditions, findings from slit-lamp biomicroscopy examination, conjunctival redness grading, study drug drop comfort assessment, dilated indirect fundoscopy, and IOP measurements will be summarized descriptively using quantitative and qualitative summary statistics by treatment arm and subject visit, as appropriate. All such measurements related to safety endpoints will also be presented in a detailed subject listing.

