10.5 Sample Size

A total sample size of 280 subjects (140 subjects per arm) yields >97.5% power to establish superiority of CSF-1 to Vehicle in the percentage of study eyes demonstrating a ≥ 3 -line (15-letter) gain from baseline in BDCVA at 40 cm (Precision Vision chart) and no loss of best distance corrected VA ≥ 5 letters (ETDRS at 4m), 1-hour post each dose on Visit 3 (Day 8) assuming a response rate of 42.5% in CSF-1 and 17.5% in Vehicle using a Pearson chi-squared test with a 2-sided significance level of 0.05.

[REDACTED]

Accounting for approximately a 5% discontinuation rate, approximately 150 subjects per arm (approximately 300 total) will be randomized.

Estimates were obtained from the Phase 2 study (18-150-0006) Intent-to-Treat (ITT) population response for pilocarpine 0.4% vs. diclofenac (control), additionally imputing missing data as failures.

At least approximately 30% of subjects will have light (i.e., blue, green, gray, and hazel) iris, and at least approximately 30% will have a brown iris. The actual percentages will vary based on enrollment.

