8.2 Missing Data Handling and Sensitivity Analysis

The primary efficacy analysis and the key secondary analyses will be performed on the FAS, as described in [section 12.1](#). In the event of missing data, the primary imputation method will be Multiple Imputation (MI), using randomized treatment-based Markov Chain Monte Carlo (MCMC). Sensitivity analyses will also be performed on the primary and key secondary efficacy endpoints measured at Visit 3 (Day 8). These sensitivity analyses will be considered supportive of the primary and key secondary analyses.

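### When the worst case is not significant, the SAP's tipping-point rule reports a single stopping point that depends on which arm is changed first

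*SAP*

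**What the plan says.** Protocol Section 10.10 allows a tipping-point analysis and leaves its specification to the SAP. SAP Section 12.2 lists it as the fourth sensitivity analysis for the primary and key secondary endpoints, on the full analysis set, and defines it in steps:

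- Start, at the least favourable imputation: "First set all records in CSF-1 with missing value as failures and all records in Vehicle with missing value as successes, that is the worst" [...].
- Model, fitted to each imputed dataset: "The imputed data will be analyzed using a logistic regression model with baseline BDCVA at 40 cm as a covariate and treatment as a main" [...].
- First stop: "If the p-value is less or equal to 0.05 for the worst case, then stop there".
- Otherwise: "set the missing records as failures or successes in all possible combinations from worse case to the best case until the p-value turns", that is, "until the p-value turns from >0.05 to ≤ 0.05".

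The visible text does not say which arm is changed first, whether the arms move together, which subjects within an arm are changed, or whether the combinations beyond the stopping point are tabulated. SAP Section 8.2 gives the status of the sensitivity analyses: "These sensitivity analyses will be considered supportive of the primary and key secondary analyses". The content of the table list in SAP Section 19 is not visible in the public copy.

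**The concern.** Suppose m1 CSF-1 and m2 Vehicle responses are missing. A scenario is then a pair (a, b): the number of missing CSF-1 and of missing Vehicle subjects counted as successes. The worst case is (0, m2) and the best case is (m1, 0). Between them lies a grid of (m1+1) × (m2+1) cells with only a partial order. Raising a by one and lowering b by one are both improvements for CSF-1, and the SAP does not rank them. A rule that stops at the first significant cell therefore returns whichever cell the chosen route meets first.

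Among the four visible sensitivity analyses, this is the only one that varies the missing-data assumption by degrees. The other three are an all-failure imputation and two observed-data analyses. Its purpose is to show how unfavourable the missing responses must be before significance is lost. A single stopping cell from an unstated route answers that incompletely, and two competent programmers could report different answers from the same data.

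**Working it through.** **The plan's own figure.** Protocol Section 10.5 claims more than 97.5% power with 140 per arm, "assuming a response rate of 42.5% in CSF-1 and 17.5% in Vehicle", "using a Pearson chi-squared test with a 2-sided significance level of 0.05". With p̄ = (0.425 + 0.175)/2 = 0.30:

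power = Φ{[0.25·√140 − 1.960·√(2·0.30·0.70)] / √(0.425·0.575 + 0.175·0.825)} = Φ{(2.958 − 1.270)/0.6235} = Φ(2.71) = 99.7%.

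The claim holds as an inequality. Inflating for 5% discontinuation gives 140/0.95 = 147.4, or 148, consistent with about 150 per arm. The documents give no figure for the tipping-point analysis itself.

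**Inputs for the example.** 150 per arm comes from Protocol Section 10.5. Eight missing per arm is an assumption (5% of 150 = 7.5). Observed responders of 43/142 (30.3%) and 27/142 (19.0%) are also an assumption, chosen so that the observed result is significant (p = 0.029) but the worst case is not.

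**Formula.** For cell (a, b), let x1 = 43 + a and x2 = 27 + b. Then ln OR = ln{x1(150 − x2)/[(150 − x1)x2]}, SE = √[1/x1 + 1/(150 − x1) + 1/x2 + 1/(150 − x2)], and p is the two-sided Wald value. This omits the baseline covariate; a check with it follows below.

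**Worst case (0, 8).** x1 = 43, x2 = 35; OR = 43·115/(107·35) = 1.32; z = 0.278/0.264 = 1.05; p = 0.293. The search therefore runs.

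**Three routes that all obey the rule:**

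| Route | First cell with p ≤ 0.05 (CSF-1, Vehicle) | x1, x2 | OR | p |
|---|---|---|---|---|
| CSF-1 changed first | 8/8, 8/8 | 51, 35 | 1.69 | 0.042 |
| Vehicle changed first | 0/8, 1/8 | 43, 28 | 1.75 | 0.043 |
| Both together | 4/8, 4/8 | 47, 31 | 1.75 | 0.036 |

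**The whole grid.** It has 9 × 9 = 81 cells, of which 32 (40%) have p > 0.05. All 32 have more successes among the missing Vehicle subjects than among the missing CSF-1 subjects. Every equal-count cell, from (0, 0) to (8, 8), is significant (p from 0.030 to 0.042). Each of the three stopping cells borders a non-significant cell: (7, 8) has p = 0.056, (0, 2) has p = 0.060 and (4, 5) has p = 0.0504. They are points along one boundary. The observed rates imply 8·43/142 = 2.4 and 8·27/142 = 1.5, so about (2, 2), where p = 0.033. None of the three routes stops there.

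**Other assumed data.** The split between CSF-1-first and Vehicle-first stopping points recurs:

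| Missing per arm | Observed responders | CSF-1 first | Vehicle first |
|---|---|---|---|
| 5 | 42/145 vs 25/145 | (3, 5) | (0, 2) |
| 8 | 42/142 vs 25/142 | (7, 8) | (0, 2) |
| 10 | 44/140 vs 24/140 | (6, 10) | (0, 5) |
| 15 | 46/135 vs 24/135 | (9, 15) | (0, 7) |

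Adding a simulated baseline covariate to the logistic model in the second row gives (6, 8) against (0, 3). Which subjects are switched within a cell moves p only slightly, for example from 0.044 to 0.050 at (3, 6). The route is the main source of the difference.

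**How often the search would run.** At the planning rates with 8 missing per arm, the expected counts are 60/142 and 25/142. The worst case is 60/150 against 33/150, with p = 0.0009, and the rule ends there. For 5, 10, 15 and 20 missing per arm, the worst-case p is 0.00008, 0.0014, 0.027 and 0.14. Simulating responders at the planning rates, the chance of a non-significant worst case is 1.7%, 5.5% and 35% for 5, 8 and 15 missing per arm. If the true CSF-1 rate were 35% (an assumption) against 17.5%, it would be about 41% with 8 missing.

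**The case against.** The strongest reply is that little depends on this. The worst case is fixed, does not depend on any order, and is tested first. At the planning rates with about 5% missing it is usually significant, and the rest of the rule is never used. When the search does run, the p-value of each cell is the same whatever the route. In the example the routes also agree on the comparison between arms: significance is lost only if missing Vehicle subjects do better than missing CSF-1 subjects. A reader might infer that the rule yields contradictory results, but the documents do not support that. The stopping cells are different points on one frontier, so the output is non-reproducible and incomplete, not self-contradictory.

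A reader might also infer that the robustness of the key secondary endpoints could not be judged. That goes too far. Section 12.2 plans three other sensitivity analyses for the same endpoints, and the worst-case odds ratio, interval and p-value are unambiguous. Nor can it be asserted that the other combinations would stay hidden: the text refers to all possible combinations, and the table list is not visible. All of this stands.

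It does not remove the gap. The governing text names a stopping rule without an order, and a stop at the first significant cell does not commit the analyst to the rest of the grid. The planning rates are stated for 1 hour after each dose. Two of the three key secondaries are measured at 2 hours, where no planning rate is visible.

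**Conclusion.** The point holds in a limited form. When responses are missing in both arms and the worst case is not significant, the SAP's rule does not determine a unique tipping point, and the single cell it returns describes only part of the frontier. In the assumed example the reported cell ranges from every missing subject responding to a single Vehicle responder among the 16 missing.

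The practical reach is small at the planning rates with 8 missing per arm (about 5 to 6% of trials) and grows with weaker effects or more missing data. These figures rest on assumed missing counts and response rates, and mostly on Wald tests without the baseline covariate.

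A reader might infer that choosing the route after unmasking could change the trial's conclusion. It could not: success and the hierarchy rest on the analysis in SAP Section 12.1, and this analysis is supportive only. It is worth correcting because the correction is cheap and removes the order dependence entirely.

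**What to change.** In SAP Section 12.2, keep the worst-case step. For any endpoint whose worst case has p > 0.05, replace the stop "until the p-value turns from >0.05 to ≤ 0.05" with the following:

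- Analyse all (m1+1) × (m2+1) combinations of CSF-1 and Vehicle successes among the missing, and tabulate the odds ratio and p-value for every cell.
- Mark the p = 0.05 frontier, counting only cells whose odds ratio favours CSF-1, since the present stopping rule states no direction.
- Mark the cell implied by the observed response rate in each arm, so that the reader can see how far it lies from the frontier.
- State a fixed rule for which subjects are set to success within a cell, because the model adjusts for baseline. Repeated random draws are optional, given how little the choice moved p in the check.

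The cost is a change of wording, a short program loop (81 fits in the example) and one larger table per endpoint. The primary test and the testing hierarchy are unaffected.
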